5.3.1.2. Between groups assessment

Exploratory comparisons between the pooled RSV vaccine group and the pooled comparator group will be done in terms of the percentage of subjects, overall doses, reporting any Grade 2/3 AE during the 7-day follow-up period (Day 1-7) after vaccination, and/ or any fever $>39.0^{\circ}\text{C}$ during the 7-day follow-up period (Day 1-7) after vaccination, and/ or any vaccine-related SAE during the 7-day follow-up period (Day 1-7) after vaccination.

The standardized asymptotic 95% CI for the difference between the pooled RSV group and (minus) the pooled comparator group will be computed.

The standardized asymptotic 95% CI for the following differences will be computed:

- RSV1D minus COMP_PLB
- RSV2D minus COMP_PLB

5.3.2. Additional considerations

Descriptive summary of the number of days with solicited local/general adverse event during the 7 day (Days 1-7) post-vaccination period will be presented.

Percentage of subjects reporting fever (any and grade 3) and other solicited general adverse events (any grade, grade 2,3 and grade 3) during the 7-day (Days 1-7) post-vaccination period by maximum intensity will be presented in figure.

Percentage of subjects reporting solicited local adverse events (any grade, grade 2,3 and grade 3) during the 7-day (Days 1-7) post-vaccination period by maximum intensity will be presented in figure.

5.3.2.1. Combined Solicited and Unsolicited Adverse Events

A summary of subjects with all combined solicited (regardless of their duration) and unsolicited adverse events will be provided. Solicited adverse events will be coded by MedDRA as per the following codes

Solicited symptom	Lower level term name	Lower level term code	Corresponding Primary Term code
Pain	Pain	10033371	10033371
Redness	Erythema	10015150	10015150
Swelling	Swelling	10042674	10042674
Drowsiness	Drowsiness	10013649	10013649
Fever	Fever	10016558	10016558
Irritability/Fussiness	Irritability	10022998	10022998
Loss of appetite	Appetite lost	10003028	10003028

For clinical.gov and EudraCT posting purposes, a summary of combined solicited and unsolicited non-serious adverse events will be produced by System Organ Class and preferred terms and according to occurrence of each event.

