5.3.2.3. Solicited Adverse Events

All analyses will be based on the ‘as treated’ analysis set. Solicited adverse events will be reported daily during the 7-day (from Day 1 to Day 7) follow up period after each vaccination, using structured diaries.

In order to summarize the data, the maximum intensity of local injection site redness/swelling (in mm) and fever (in $^{\circ}\text{C}$) will be categorized as follows:

Grading	Redness/swelling	Fever
0:	None	$< 38.0^{\circ}\text{C}$ (100.4°F)
1:	< 5 mm	$\geq 38.0^{\circ}\text{C}$ (100.4°F) - $\leq 39.0^{\circ}\text{C}$ (102.2°F)
2:	$> 5 - \leq 20$ mm	$> 39.0^{\circ}\text{C}$ (102.2°F) - $\leq 40.0^{\circ}\text{C}$ (104.0°F)
3:	> 20 mm	$> 40.0^{\circ}\text{C}$ (104.0°F)

Fever is defined as temperature $\geq 38.0^{\circ}\text{C} / 100.4^{\circ}\text{F}$ (regardless of the location of measurement). The preferred location for measuring temperature in this study will be the oral cavity. Body temperature will also be summarized by 0.5°C increments as follows: $\geq 38.0, >38.5, >39.0, >39.5, >40.0^{\circ}\text{C}$.

For each of the time points or time intervals presented in the summaries, only subjects with at least one plausible observation (i.e., any non-missing values but excluding “Not done/unknown” and implausible values) for the solicited adverse events in the interval of interest will be considered. Subjects without plausible data (i.e. missing values or reported as “Not done/unknown” and implausible values) will be removed from the denominator to prevent a downward bias (towards zero).

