9.4. Coding for the AE of specific interest

Any of the below listed preferred term reported as an Expedited Adverse Event must be immediately escalated to the CRDL or Central Safety Physician to assess or confirm the need for an urgent IDMC review.

The list of preferred terms and associated PT codes is given below:

HAEMATOMA

Preferred term	PT code
abdominal wall haematoma	10067383
administration site haematoma	10075100
adrenal haematoma	10059194
aortic intramural haematoma	10067975
application site haematoma	10068317
arterial intramural haematoma	10074971
auricular haematoma	10003797
basal ganglia haematoma	10077031
brain stem haematoma	10073230
breast haematoma	10064753
broad ligament haematoma	10006375
bursal haematoma	10077818
catheter site haematoma	10055662
cephalhaematoma	10008014
cerebellar haematoma	10061038
cerebral haematoma	10053942
cervix haematoma uterine	10050020
chest wall haematoma	10076597
colonic haematoma	10009996
deep dissecting haematoma	10074718
extradural haematoma	10015769
eyelid haematoma	10064976
haematoma	10018852
haematoma evacuation	10060733
haematoma infection	10051564
hepatic haematoma	10019676
incision site haematoma	10059241
infusion site haematoma	10065463
injection site haematoma	10022066
instillation site haematoma	10073609
intestinal haematoma	10069829
intra-abdominal haematoma	10056457
intracerebral haematoma evacuation	10062025

Preferred term	PT code
intracranial haematoma	10059491
intraocular haematoma	10071934
laryngeal haematoma	10070885
lip haematoma	10066304
mediastinal haematoma	10049941
medical device site haematoma	10075577
mesenteric haematoma	10071557
nasal septum haematoma	10075027
oesophageal intramural haematoma	10077486
oral mucosa haematoma	10074779
ovarian haematoma	10033263
paranasal sinus haematoma	10069702
pelvic haematoma	10054974
penile haematoma	10070656
perineal haematoma	10034520
periorbital haematoma	10034544
periosteal haematoma	10077341
perirenal haematoma	10049450
peritoneal haematoma	10058095
pharyngeal haematoma	10068121
post procedural haematoma	10063188
pulmonary haematoma	10054991
renal haematoma	10038459
retroperitoneal haematoma	10058360
scrotal haematoma	10039749
spinal cord haematoma	10076051
spinal epidural haematoma	10050162
spinal subdural haematoma	10050164
splenic haematoma	10041646
spontaneous haematoma	10065304
subarachnoid haematoma	10076701
subcutaneous haematoma	10042345
subdural haematoma	10042361
subgaleal haematoma	10069510
subretinal haematoma	10071935

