10.1.3.12. Counting rules for combining solicited and unsolicited adverse events

For output combining solicited and unsolicited adverse events, all serious adverse events will be considered general events since the administration site flag is not included in the expedited adverse event CRF pages.

Multiple events with the same preferred term which start on the same day are counted as only one occurrence.

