N = number of subjects with at least one administered vaccination

n/% = number/percentage of subjects who took the specified type of concomitant medication at least once during the considered period

95% CI = Exact 95% confidence interval; LL = lower limit, UL = upper limit

Template 29 Summary of occurrences and subjects with at least one solicited and unsolicited adverse event classified by MedDRA Primary System Organ Class and Preferred Term with onset within 30 days of first and second vaccination – SAE excluded <RSV 1D, RSV 2D, Comparator/Placebo> groups (Exposed Set)

Primary System Organ Class (CODE) Preferred Term (CODE)	<Group 1> N=XXXX			<Group 2> N=XXXX		
	occ	n	%	occ	n	%
Any solicited and unsolicited adverse event	XXX	XXX	XX.X	XXX	XXX	XX.X
<SOC 1 (code)>	XXX	XXX	XX.X	XXX	XXX	XX.X
<Preferred Term 1 (code)>	XXX	XXX	XX.X	XXX	XXX	XX.X
<Preferred Term 2 (code)>	XXX	XXX	XX.X	XXX	XXX	XX.X
<SOC 2 (code)>	XXX	XXX	XX.X	XXX	XXX	XX.X
<Preferred Term 1 (code)>	XXX	XXX	XX.X	XXX	XXX	XX.X
<Preferred Term 2 (code)>	XXX	XXX	XX.X	XXX	XXX	XX.X

Short group label = long group label

Any adverse event = at least one adverse event experienced (regardless of the MedDRA Preferred Term)

N = number of subjects with at least one administered vaccination

n* = number of events reported

n/% = number/percentage of subjects reporting the adverse event at least once

95% CI = exact 95% confidence interval; LL = Lower Limit, UL = Upper Limit

Template 30 Number (%) of subjects with serious adverse events <from Day 1 up to <Day 61/end of second RSV season>, including number of events reported for pooled RSV 1D, RSV 2D and Comparator/Placebo> groups (Exposed Set)

			<Each group> N=XXXX			<Each group> N=XXXX		
Type of Event	Primary System Organ Class (CODE)	Preferred Term (CODE)	n*	n	%	n*	n	%
SAE		At least one symptom	xxx	xxx	xx.x	xxx	xxx	xx.x
	<each SOC (SOC code)>	<each PT (PT code)>	xxx	xxx	xx.x	xxx	xxx	xx.x
			xxx	xxx	xx.x	xxx	xxx	xx.x
Related SAE		At least one symptom	xxx	xxx	xx.x	xxx	xxx	xx.x
	<each SOC (SOC code)>	<each PT (PT code)>	xxx	xxx	xx.x	xxx	xxx	xx.x
			xxx	xxx	xx.x	xxx	xxx	xx.x
Fatal SAE		At least one symptom	xxx	xxx	xx.x	xxx	xxx	xx.x
	<each SOC (SOC code)>	<each PT (PT code)>	xxx	xxx	xx.x	xxx	xxx	xx.x
			xxx	xxx	xx.x	xxx	xxx	xx.x
Related Fatal SAE		At least one symptom	xxx	xxx	xx.x	xxx	xxx	xx.x
	<each SOC (SOC code)>	<each PT (PT code)>	xxx	xxx	xx.x	xxx	xxx	xx.x
			xxx	xxx	xx.x	xxx	xxx	xx.x

Short group label = long group label

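### The registry-posting adverse-event table shows injection-site pain, redness and swelling under general term names, in the same rows as unsolicited events elsewhere on the body coded to the same terms

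*SAP*

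**What the plan says.** SAP Section 5.3.2.1 provides for a summary combining solicited and unsolicited events and says "Solicited adverse events will be coded by MedDRA as per the following codes". The three local symptoms appear in the coding table as "Pain Pain 10033371 10033371", "Redness Erythema 10015150 10015150" and "Swelling Swelling 10042674 10042674" (symptom, lower level term, lower level code, primary term code). None carries an injection-site or administration-site qualifier.

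The same section requires a non-serious version by system organ class and preferred term for registry posting. The matching mock table is Template 29, titled in part "Summary of occurrences and subjects with at least one solicited and unsolicited adverse event classified by MedDRA Primary System Organ Class". Its only rows are classes and preferred terms, and its columns are occurrences, subjects and percentage.

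Section 10.1.3.12, which governs outputs combining the two kinds of event, adds: "Multiple events with the same preferred term which start on the same day are counted as only one occurrence". It sets no condition on site.

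**The concern.** Elsewhere the SAP treats these three symptoms as local reactions. Section 5.3.2.3 grades redness and swelling by their size at the injection site, and Template 16, the table of solicited local events, has blocks for Pain and for Swelling/Redness. The coding step removes that information, and Template 29 has nothing to restore it.

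What is at stake is how the public record reads. Section 7.1 lists web disclosure for the Day 61 and end-of-second-season analyses. Template 29 covers 30 days after the first and second vaccinations. In that window the arms receive different injections by design (SAP Table 1): RSV vaccine then buffer, RSV vaccine twice, or a licensed vaccine and buffer in an order that depends on the comparator, with buffer only under placebo. Any difference in local reactogenicity would be posted as a difference in Erythema or Swelling, which an outside reader could take for an event not tied to the injection site.

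**Working it through.** The SAP gives no event rates for this table, so the check is mainly a matter of following its rules.

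**Tracing an event**

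1. An infant has solicited redness at the injection site. Section 5.3.2.1 codes it to Erythema.
2. The same or another infant has non-serious unsolicited erythema elsewhere, coded to Erythema. Section 5.3.2.4 maps investigators' verbatim terms to preferred terms.
3. Template 29 places both in one Erythema row. It has no local/general split, no solicited/unsolicited split and no footnote separating them.
4. If both occur in one infant and start on the same day, Section 10.1.3.12 counts one occurrence.

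The same path holds for Pain and Swelling, so 3 of the 7 solicited symptoms are affected. The other four (drowsiness, fever, irritability/fussiness, loss of appetite) are general symptoms and raise no site question.

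**Is the site information available?** Section 10.1.3.12 explains that serious events are treated as general because the expedited pages lack an administration-site flag. This implies that the flag exists on the non-serious pages. Template 29 excludes serious events, so the flag should cover the unsolicited events in scope. Section 5.3.1.1 supports this: it tabulates local and general events, each solicited and unsolicited, which requires a site class for unsolicited events.

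**Does the dictionary separate site?** Section 9.4 lists "injection site haematoma" and similar vaccination-site and administration-site terms, so site-qualified preferred terms exist at least for haematoma and haemorrhage.

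**Illustration of size.** The rates are assumptions: local redness in 20 to 40% of infants and unsolicited erythema elsewhere in 1 to 2%, in different infants. SAP Table 2 gives a target of 50 subjects per pooled arm.

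- Local: 50 × 0.20 = 10 to 50 × 0.40 = 20 infants.
- Elsewhere: 50 × 0.01 = 0.5 to 50 × 0.02 = 1 infant.
- Local share of the Erythema row: lowest 20 / (20 + 2) = 90.9%, highest 40 / (40 + 1) = 97.6%.
- Doubling the general event from 2% to 4% moves the row by 2 percentage points, or one infant in 50.

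**Same-day collapse.** At the upper assumed rates, and if the two events are independent, 50 × 0.40 × 0.02 = 0.4 infants per arm would have both, before requiring the same start day. Section 10.1.3.13 counts a solicited event once per period, so each coincidence loses at most one occurrence.

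**The case against.** The strongest reply is that Template 29 is a disclosure summary under additional considerations, and that its components are reported separately elsewhere. Template 16 gives solicited local reactions. Template 21 gives unsolicited events by class and preferred term with exact 95% intervals, and Template 56 gives the unsolicited categories. Template 15 splits any, local and general events. The primary endpoints in Section 3.2.1 list solicited events, unsolicited events, serious events and bleeding as separate items. The comparisons in Section 5.3.1.2 use any Grade 2/3 event, fever and related serious events, none of which depends on the preferred term of a local symptom. All of this stands and limits the point to the combined output.

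A reader might infer that frequent local reactions would hide an excess of general erythema or swelling from the trial's analyses. The SAP does not support that: unsolicited erythema appears in Template 21, undiluted by solicited redness.

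A reader might also infer an error from the primary term code equalling the lower level code in all seven rows. Identical codes are not wrong in themselves. Whether any row is wrong depends on the dictionary hierarchy, which the SAP does not show.

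Two smaller replies also have force. Section 9.4 does not show that site-specific terms exist for pain, erythema and swelling. The title of Template 29 does tell the reader that solicited events are included, but it does not say which rows hold local reactions.

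**Conclusion.** The point holds as a defect of coding and labelling in one type of output. Followed as written, the plan posts injection-site pain, redness and swelling under unqualified names and cannot separate them, in that table, from events elsewhere coded to the same terms. The naming problem arises whenever a local reaction is reported. Actual merging also needs an unsolicited non-serious event with the same preferred term.

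The effect on percentages in the posted rows could be large relative to the general component, as the assumed rates show, but those rates are not from the SAP. The undercount of occurrences is probably very small. No primary endpoint, analysis set or planned between-group comparison changes.

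**What to change.** Take one of two routes in Section 5.3.2.1 and Template 29:

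- Code the three local symptoms to the injection-site or administration-site terms of the dictionary version in use, after checking that those terms exist there.
- Keep the present terms and split Template 29 into local and general rows, using solicited-local status and, for unsolicited events, the administration-site flag. Confirm first that the flag is on the non-serious event pages.

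In either case, amend Section 10.1.3.12 so that same-day events with the same term are collapsed only within local or within general events.

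The cost is a small change to one coding table or one mock table, one line of the counting rules, and the related programming. If the flag is confirmed, no change to data collection is needed.

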5.3.2.2. Exclusion of implausible solicited Adverse Event

Some local and systemic adverse events will be directly measured by the subject and will not be subject to a reconciliation process, even if they are biologically implausible. Therefore, these implausible measurements will be removed from the analysis but included in listings. Implausible measurements are summarized in the table below:

Table 5 Implausible Solicited Adverse Events

Parameter	Implausible measurements
Body temperature	$\leq 33^{\circ}\text{C}$ or $\geq 42^{\circ}\text{C}$
Swelling	For subjects < 6 years: ≥ 250 mm Measurements < 0 mm

5.3.2.3. Solicited Adverse Events

All analyses will be based on the ‘as treated’ analysis set. Solicited adverse events will be reported daily during the 7-day (from Day 1 to Day 7) follow up period after each vaccination, using structured diaries.

In order to summarize the data, the maximum intensity of local injection site redness/swelling (in mm) and fever (in $^{\circ}\text{C}$) will be categorized as follows:

Grading	Redness/swelling	Fever
0:	None	$< 38.0^{\circ}\text{C}$ (100.4°F)
1:	< 5 mm	$\geq 38.0^{\circ}\text{C}$ (100.4°F) - $\leq 39.0^{\circ}\text{C}$ (102.2°F)
2:	$> 5 - \leq 20$ mm	$> 39.0^{\circ}\text{C}$ (102.2°F) - $\leq 40.0^{\circ}\text{C}$ (104.0°F)
3:	> 20 mm	$> 40.0^{\circ}\text{C}$ (104.0°F)

Fever is defined as temperature $\geq 38.0^{\circ}\text{C} / 100.4^{\circ}\text{F}$ (regardless of the location of measurement). The preferred location for measuring temperature in this study will be the oral cavity. Body temperature will also be summarized by 0.5°C increments as follows: $\geq 38.0, >38.5, >39.0, >39.5, >40.0^{\circ}\text{C}$.

For each of the time points or time intervals presented in the summaries, only subjects with at least one plausible observation (i.e., any non-missing values but excluding “Not done/unknown” and implausible values) for the solicited adverse events in the interval of interest will be considered. Subjects without plausible data (i.e. missing values or reported as “Not done/unknown” and implausible values) will be removed from the denominator to prevent a downward bias (towards zero).

5.3.2.4. Unsolicited Adverse Events

All the unsolicited adverse events occurring during the study, judged either as related, or not related to vaccination by the investigator, will be recorded. All the unsolicited adverse events/AE of specific interest (Spontaneous or excessive bleeding) occurring during the 30-day (Day 1 to Day 30) follow up period after each vaccination, and all serious adverse events/AE of specific interest (RSV LRTI) occurring from Dose 1 up to study end will be recorded according to the protocol-specified reporting rules. The original verbatim terms used by investigators to identify adverse events in the CRFs will be mapped to preferred terms using the MedDRA dictionary. The unsolicited adverse events will then be grouped by MedDRA preferred terms into frequency tables according to system organ class. Adverse events judged by the investigator as at least possibly related to study vaccine will be summarized by vaccine group, according to system organ class and preferred term within system organ class. When an unsolicited adverse event occurs more than once for a subject, the maximal severity and strongest relationship to the vaccine group will be counted.

Only vaccine-emergent adverse events will be analyzed, i.e., excluding those after a subject has given informed consent but before vaccination. The selection of unsolicited adverse events and the assignment to time intervals will be done by day of onset and not by days ongoing/persisting.

The analysis of unsolicited adverse events during the 30-day post vaccination period includes the following categories:

- Any unsolicited adverse event.
- Possibly related unsolicited adverse events.
- Grade 3 unsolicited adverse events
- Grade 3 related unsolicited adverse events.
- Serious adverse events (SAEs)
- Possibly related SAEs.
- Medically attended adverse events
- AE of specific interest (spontaneous or excessive bleeding)

SAE and AE of specific interest (RSV-LRTI) has to be reported from Day 1 up to Day 61, from Day 1 to end of 1st RSV season and from Day 1 to end of 2nd RSV season.

5.4. Analysis of RTI and LRTI

5.4.1. Analysis of RTI and LRTI planned in protocol

The primary analysis will be performed on the ES of subjects with a negative RSV exposure status (at screening based on in-stream baseline serological testing) in the pooled single dose RSV vaccine group, the pooled two dose RSV vaccine group, and the pooled comparator group separately for first and second RSV seasons and overall. A similar analysis will be performed on the entire ES. As primary analysis, the assessment of RSV infection will be performed using the quantitative RT-PCR according to standardized case definitions (see Table 6 of the SAP) based on the available WHO case definitions.

The number of RSV infections within each group and the maximum disease severity of the event will be tabulated. The rate (with 95% CI) of RSV-RTI and RSV-LRTI and infections progressing to hospitalization will be evaluated for each of the three pooled groups.

The rate of very severe RSV-LRTI among RSV infected infants with a negative RSV exposure status (at screening based on in-stream baseline serological testing) from first vaccination (Day 1) up to the end of the first RSV transmission season will be estimated as well as 95% one-sided lower CI.

The proportion and the relative risk of subjects with at least one RSV-associated RTI (with 95% CI) between each of two pooled RSV vaccine groups and the pooled control group will be calculated for both the cohort of subjects with a negative RSV exposure status (at screening based on in-stream baseline serological testing) on the ES and on the entire ES. The same descriptive analysis will be performed for subjects with at least one RSV-associated LRTI and those with at least one RSV-associated severe LRTI.

Descriptive analyses (mean, median, min, max) of viral load assessed by the quantitative RT-PCR (RSV-A/B) of all cases as listed in Table 6 of the SAP will be tabulated by case category. This analysis will also be done on the three pooled groups.

The incidence rate of all cases as listed in Table 6 of the SAP (with 95% CI) will be calculated by the three pooled groups. The same descriptive analysis will be performed for all cause LRTI and all cause severe LRTI. These will also be presented for each viral etiology identified by the multiplex PCR.

The incidence rate of asymptomatic RSV infections (with 95% CI) detected by the quantitative PCR (RSV-A/B), will be tabulated by the three pooled groups. Descriptive analyses (mean, median, min, max) of viral load assessed by the quantitative RT-PCR (RSV-A/B) of those asymptomatic RSV infections will also be done on the three pooled groups.

The RVP (Multiplex PCR) on specimens from all RSV-A/B positive and confirmed LRTI cases, according to case definition presented in Table 6 (Figure 3 of the protocol for the decision tree), will be tabulated as a qualitative assessment profiling the potential co-infections occurring in these subjects.

